### **Subject Information**

*Target accrual is the proposed total number of subjects to be included in this study at Mayo Clinic. A “Subject” may include medical records, images, or specimens generated at Mayo Clinic and/or received from external sources.*

Target accrual: 50 historic patients for baseline metric; 50 current intervention patients to undergo simulation session.

Subject population (children, adults, groups): Adult

Inclusion Criteria: Baseline normal neurological function pre-operatively, planned use of mechanical ventilator with endotracheal tube post-operatively after planned cardiothoracic surgical procedure. Age: greater than 18 and less than 60.

**Exclusion Criteria:** Chronic dementia, Alzheimer's disease, or other chronic neurological disease (i.e. Bi-Polar). Chronic use of neurological altering medications such as benzodiazepines, psychotropic, anti-depressants, anxiolytics. Patient undergoing emergent surgery. Use of post-operative cardiopulmonary support devices such as ECMO (extracorporeal membrane oxygenation), intra-aortic balloon pump, total artificial heart, or other similar device. Age greater than 60; Age less than 18. Previous admission to an intensive care unit (intervention patients).

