## Research Question and Aims

Hypothesis: A pre-ICU simulation session will decrease the incidence and severity of post-operative delirium in the ICU after an elective cardiothoracic surgical procedure.

Aims, purpose, or objectives: The purpose of this project is to evaluate the effect of a pre-ICU admission simulation session on post-operative delirium in the elective cardiothoracic surgical population,

Background (*Include relevant experience, gaps in current knowledge, preliminary data, etc.*):

Cardiothoracic patients are at a high risk for post-operative delirium in the intensive care unit (ICU). Approximately 50% of patients admitted to the intensive care unit develop or are impacted by some form of acute delirium. This can lead to a three-fold increase in 6-month mortality, increased time on the mechanical ventilator, elongated hospital length of stay, and nearly 50% of those patients affected having a cognitive impairment at hospital discharge some with long term cognitive impairment (approximately 1 in 3 patients). Specifically, delirium incidence in the post-cardiac surgery population is between 26-52%. Delirium in this population specifically has been associated with increased mortality, stroke risk, hospital readmission and cognitive dysfunction as well as poorer functional status.

The literature supports the use of pre-operative educational experiences as a mechanism to reduce delirium incidence.

The initial phase of this project is to identify the baseline rate of delirium in the cardiothoracic surgical intensive care unit. Anecdotal data from practitioners in this unit indicate that post-operative delirium across “surgical procedure types” is a strong concern. A primary gap in this population’s care is that our institution does not have a program in place to prepare patients for the experience they will have admitted to the ICU post-operatively.

The initial phase of this project will include baseline data collection over a period of 3 months to determine current delirium rates (CAM-ICU) and other ICU outcome metrics including ventilator time, use of sedatives and antipsychotics, restraint use rates, and ICU and hospital length of stay.

Following initial baseline data collection, the intervention will be to provide a pre-cardiothoracic surgery patient a multi-sensory pre-recorded virtual reality ICU simulation experience to introduce them to the senses they can

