expect to encounter post-operatively when admitted to the critical care unit. This is intended as a mechanism to reduce post-operative delirium in this population by allowing them to “become familiar” with the sights/sounds/tactile experiences in the ICU so that they are not completely foreign to the patient upon admission post-operatively.

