## Study Design and Methods

**Methods:** *Describe in lay terms, completely detailing the research activities that will be conducted by Mayo Clinic staff under this protocol.*

Data collection and Outcome Metrics :

- CAM-ICU scores in the post-operative setting
- Incidence of acute delirium in the post-operative setting
- Time of intravenous sedation in the post-operative setting
- Time of mechanical ventilator in the post-operative setting
- Incidence of anti-psychotic medication administration to treat delirium
- Incidence and duration of cardiopulmonary bypass “pump time”
- Metrics will be stratified based on type of operative procedure, operative time, age, gender, necessity for return to operating room prior to initial extubation

The data source will be the electronic medical record. Baseline retrospective data will be collected on patients prior recorded prior to the start date of this IRB submission; prospective patients undergoing simulation session will have data recorded post IRB start date. Data collection form attached with IRB submission.

Charts of all initial post cardiac surgery patients admitted directly to the ICU who meet the above criteria will be reviewed.

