### Data Analysis

*Power analyses may not be appropriate if this is a feasibility or pilot study, but end-point analysis plans are always appropriate even if only exploratory. Provide all information requested below, or provide justification if not including all of the information.*

**Power Statement:** Based on the literature indicating incidence of post-operative delirium in the post cardiothoracic surgical population and initial power analysis calculations, initial calculations indicate sample size of approximately 30 patients. Therefore, to accommodate for patient loss to follow-up will aim for sample size of 50 patients.

**Data Analysis Plan:** A comparative analysis of the outcome metrics described in the "Study Design and Methods" section will be completed between the pre-implementation baseline data and the post-implementation intervention data. This analysis will evaluate the effect of the multi-sensory ICU simulation experience on post-operative delirium in the cardiac surgical population. An additional post-implementation interview/survey will be conducted on post-intervention patients as described above.

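### The exclusion for a previous ICU stay applies only to intervention patients, so the historic controls may differ on ICU familiarity, the factor the simulation is meant to change

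*Protocol*

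**What the plan says.** Subject Information in the Protocol gives one eligibility list for 50 historic and 50 intervention patients. Its last exclusion is "Previous admission to an intensive care unit (intervention patients"). No other criterion names a group, and nothing elsewhere applies a previous-ICU rule to the historic patients.

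Study Design and Methods describes how the controls are found:

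- "Baseline retrospective data will be collected on patients prior recorded prior to the start date of this IRB submission".
- "Charts of all initial post cardiac surgery patients admitted directly to the ICU who meet the above criteria will be reviewed".

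The stratification factors in the same section are type of procedure, operative time, age, gender and return to the operating room before first extubation. Previous ICU admission is not among them.

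Research Question and Aims says the ICU experiences are introduced beforehand "so that they are not completely foreign to the patient upon admission post-operatively". Data Analysis then compares outcomes "between the pre-implementation baseline data and the post-implementation intervention data".

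**The concern.** This is a non-randomised before-after study, and the baseline-versus-intervention contrast is its only comparative evidence on delirium. Any difference in eligibility between the groups feeds directly into that contrast.

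This difference lies on the hypothesised pathway. If familiarity with the ICU lowers delirium, a real ICU stay is a plausible source of it. The plan screens that source out of the treated group and leaves it open in the comparator.

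The direction of any bias cannot be known in advance:

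- **Masking.** Controls familiar with the ICU may have less delirium, which would hide a benefit.
- **Exaggeration.** Controls with an earlier ICU stay may be sicker and have more delirium, which would create or enlarge an apparent benefit.

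Adjustment cannot fully repair this, because the intervention group contains no patients with an earlier stay.

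**Working it through.** The plan gives no figure on this point, so there is none to reproduce. The check asks how large the bias could be.

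**Inputs from the Protocol**
- Group sizes: 50 and 50 (Subject Information).
- Delirium rate: "delirium incidence in the post-cardiac surgery population is between 26-52" percent (Research Question and Aims). I use the ends and the midpoint: 26%, 39%, 52%.

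**Assumptions, not in the Protocol**
- f, the share of controls with an earlier ICU stay: 5% to 30%.
- RR, their delirium risk relative to other controls: 1.5 or 2 (sicker), 0.67 (familiar).
- Test: two-sided 5% chi-square without continuity correction, with rejection probabilities by exact enumeration of both binomials.

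These are illustrations, not bounds.

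**Formula.** With p the rate in patients without an earlier stay and no true effect:

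control rate = (1 − f)·p + f·p·RR, so spurious difference = f·p·(RR − 1).

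Example: 0.10 × 0.26 × 0.5 = 0.013, or 1.3 points.

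**Exaggeration: no true effect, 50 vs 50**

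| p | f | RR | Control rate | Chance of false benefit |
|---|---|---|---|---|
| 26% | 0 | – | 26.0% | 2.5% |
| 26% | 5% | 1.5 | 26.65% | 3.0% |
| 26% | 10% | 1.5 | 27.3% | 3.5% |
| 26% | 30% | 2 | 33.8% | 13.3% |
| 39% | 0 | – | 39.0% | 2.6% |
| 39% | 5% | 1.5 | 40.0% | 3.3% |
| 39% | 10% | 1.5 | 41.0% | 4.1% |
| 39% | 30% | 2 | 50.7% | 23.1% |
| 52% | 0 | – | 52.0% | 2.8% |
| 52% | 10% | 1.5 | 54.6% | 5.0% |
| 52% | 30% | 1.5 | 59.8% | 12.9% |

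RR 2 is impossible at 52%, since 2 × 52% exceeds 100%.

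**Masking: true rates 52% vs 26%, RR 0.67**

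| f | Observed control rate | Power |
|---|---|---|
| 0 | 52.0% | 77% |
| 5% | 51.1% | 75% |
| 10% | 50.3% | 72% |
| 20% | 48.6% | 66% |
| 30% | 46.9% | 59% |

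**Restricting without replacing excluded controls.** Controls left = 50·(1 − f), that is 45, 40 or 35 at f = 10%, 20% or 30%. Power for 52% vs 26% is then 74%, 72% or 69%, and the chance of a false benefit at 26% stays at 2.5% to 2.6%.

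**Screening to keep 50.** Charts needed = 50/(1 − f) = 52.6, 55.6, 62.5 or 71.4 at f = 5%, 10%, 20% or 30%. Rounded up, that is 53, 56, 63 or 72.

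**The case against.** There is a real case for treating this as minor.

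- **The tag may be loose drafting.** Every historic patient already has the index ICU stay on record, so an untagged criterion, read literally, would exclude every control. That is a fair explanation of the tag. It does not restrict earlier stays in controls.
- **Intervention patients may be wanted ICU-naive for the surveys.** The survey questions on fears and on what was unfamiliar would fit that aim. The Protocol does not state this reason, and it would not justify a different rule for the comparator.
- **Other criteria limit the exposed share.** Restriction to initial post-surgical patients admitted directly, the age limit and the exclusion of emergency surgery probably remove some exposed controls. They do not exclude ICU stays for other reasons, so exposure is reduced rather than ruled out.
- **The effect is small in mild cases.** At 26%, a spurious 0.65 to 1.3 points compares with a standard error of √(2 × 0.26 × 0.74/50) = 8.8 points. The large figures need f = 30% and RR 2. This stands and limits how much weight the point carries.
- **Restriction buys little power.** At f = 10% it gives 74%, against 72% if exposed controls stay in and RR is 0.67, and 77% if RR is 1. This is correct, but the purpose of restriction is a like-for-like comparison, not power.
- **Unseen material may help.** The Protocol notes "Data collection form attached with IRB submission"; that form may record previous ICU admission. Recording it would support a later analysis but would not make the eligibility rule equal.

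**Conclusion.** The concern holds. As written, the plan puts an eligibility difference on ICU familiarity into its only comparison, and neither the chart-selection rule nor the stratification list removes it.

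The size cannot be derived from the Protocol. Under the assumed f and RR it runs from negligible (5% of controls exposed) to serious (30% exposed with RR 2). It is zero if no control is exposed or if RR is 1, and its sign is unknown. It does not invalidate the study by itself. It should be fixed because the correction is cheap and the bias could not be corrected reliably afterwards. Confidence is moderate.

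**What to change.** Reword the criterion as admission to any ICU before the index cardiothoracic surgery, and apply it to both groups. Naming the index surgery avoids excluding every control for the ICU stay under study. Screen the historic charts for it and replace each ineligible chart with the next eligible consecutive one until there are 50.

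If the charts are already abstracted, record ICU admission before the index surgery. Make the comparison among patients without it the main analysis, since that is the one stratum containing both groups, and report all controls as a sensitivity analysis.

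**Cost.** One line of text and screening of about 53 to 72 charts for f between 5% and 30%. The plan foresees "baseline data collection over a period of 3 months to determine current delirium rates". If 50 eligible charts would otherwise just fill those 3 months at an even rate (an assumption), the window grows to 3/(1 − f) months: about 3.2, 3.3, 3.8 or 4.3 at f = 5%, 10%, 20% or 30%. The fallback without replacement loses some power if there is no bias: 74% to 69% for f = 10% to 30%, against 77%.

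**Limits.** ICU stays at other hospitals may be under-recorded in historic charts, so the change reduces the imbalance and may not remove it entirely. Other before-after biases remain.

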### Review of medical records, images, specimens

The study involves data that exist at the time of IRB submission **and** data that will be generated after IRB submission. Include this activity in the Methods section.

#### Examples

- The study plans to conduct a retrospective chart review and ask subjects to complete a questionnaire.
- The study plans to include subjects previously diagnosed with a specific disease and add newly diagnosed subjects in the future.

### Data Analysis

*Power analyses may not be appropriate if this is a feasibility or pilot study, but end-point analysis plans are always appropriate even if only exploratory. Provide all information requested below, or provide justification if not including all of the information.*

**Power Statement:** Based on the literature indicating incidence of post-operative delirium in the post cardiothoracic surgical population and initial power analysis calculations, initial calculations indicate sample size of approximately 30 patients. Therefore, to accommodate for patient loss to follow-up will aim for sample size of 50 patients.

**Data Analysis Plan:** A comparative analysis of the outcome metrics described in the "Study Design and Methods" section will be completed between the pre-implementation baseline data and the post-implementation intervention data. This analysis will evaluate the effect of the multi-sensory ICU simulation experience on post-operative delirium in the cardiac surgical population. An additional post-implementation interview/survey will be conducted on post-intervention patients as described above.

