### Pre ICU Simulation Survey – Patient

1. You are going to be admitted to the intensive care unit after your surgery. What are your thoughts / feelings / fears regarding your upcoming ICU stay?

Post-ICU Simulation, intervention patients will be surveyed with the following questions:

1. What was the biggest take-home point you learned during your virtual reality ICU simulation experience?
2. How do you hope that this ICU simulation experience will impact your actual ICU experience after your cardiac surgery?

Post actual ICU experience, intervention patients will be surveyed in person with the following questions:

1. Please describe your ICU experience.

2. What do you remember from your virtual reality pre-operative ICU simulation experience?
3. Did you experience any of the things you experienced in the virtual reality ICU simulation during your actual ICU experience? Please describe.
4. How do you feel that your pre-operative virtual reality ICU simulation experience impacted your or prepared you for your actual ICU experience?
5. Did you feel that the pre-operative virtual reality ICU simulation experience was beneficial?
6. What about your actual ICU experience was unfamiliar to you?
7. How would you modify the pre-operative virtual reality ICU simulation experience to improve your actual ICU experience?

Informed consent for research will be obtained by a member of the research team in the pre-surgical clinic setting; a future date for the simulation session will then be mutually agreed upon by study staff and patient/family.

Following informed consent for research, the pre-surgical patient will be asked to view a 10 minutes pre-recorded virtual reality simulation session from the perspective of a postoperative ICU patient. This virtual reality simulation session has been recorded in the Mayo Clinic Simulation Center under the guidance of study team members from Critical Care, and Cardiothoracic surgery.

The multi-sensory ICU simulation experience will include the following:

- View on a virtual reality head set
- Introduce to different care team members
- Introduction to common equipment found in the patient room in the intensive care unit
- Introduction to common experiences, sounds, sights and procedures in the intensive care unit
- Total video duration: 10 minutes

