### Endpoints

**Primary:** Study to end when sample sizes are obtained.

**Secondary:** None.

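### Does the step from about 30 to 50 patients, put down to loss to follow-up, leave the sample size unsound?

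*Protocol*

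**What the plan says.** The Power Statement (protocol, Data Analysis) appeals to published delirium incidence and to preliminary calculations, and reports that "initial calculations indicate sample size of approximately 30 patients". It continues: "to accommodate for patient loss to follow-up will aim for sample size of 50 patients". It gives no assumed rates, alpha, sidedness, power, test or loss rate, and does not say whether 30 is per group or in total.

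The only incidence specific to this population is in Research Question and Aims: "delirium incidence in the post-cardiac surgery population is between 26-52" per cent. The same section plans three months of baseline data collection to find the unit's own rate.

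Subject Information sets the accrual: "50 historic patients for baseline metric; 50 current intervention patients to undergo simulation session". Under Study Design and Methods, "The data source will be the electronic medical record", and for the comparison group, "Baseline retrospective data will be collected on patients" treated before the IRB start date. Later contact with patients is limited to a survey: "Post actual ICU experience, intervention patients will be surveyed in person with the following questions". Endpoints says: "Study to end when sample sizes are obtained".

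**The concern.** The power statement is the only justification offered for the accrual, and both of its steps invite doubt.

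- **The 30.** The natural inputs, the two ends of the cited incidence range, do not give 30 per group in a two-group comparison. The choice of baseline rate within that range also matters a good deal.
- **The step to 50.** Follow-up loss is an awkward reason when delirium is read from the inpatient record. It cannot apply to historic charts, yet that group is set at 50 too. The implied allowance is large. If it were taken literally and fell on the intervention group alone, one could read the plan as content with 50 v 30.

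At stake would be the size of effect the study can detect, and whether the sponsor would treat 30 evaluable intervention patients as sufficient.

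**Working it through.** **Inputs.** From the protocol: incidence 26% to 52%; calculated size about 30; target 50; accrual 50 + 50. Assumed, because the protocol gives none: two-sided alpha 0.05 and 80% power unless stated otherwise, pooled normal approximation for two proportions.

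**1. Can the 30 be reproduced?** Per group,

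n = [z(1-α/2)·√(2p̄(1-p̄)) + z(power)·√(p1(1-p1)+p2(1-p2))]² / (p1-p2)².

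With p1 = 0.52, p2 = 0.26, p̄ = 0.39:

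n = [1.960·√0.4758 + 0.842·√0.4420]² / 0.26² = 54.05, so 55 per group.

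The other usual settings give 43 (one-sided, 80%), 59 (one-sided, 90%) and 72 (two-sided, 90%). None is near 30. Two other routes do reach about 30:

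- Two groups with a larger effect: 52% to 18.2%, a 65% relative fall, gives n = 30.1.
- One sample against a fixed rate: 52% to 26% gives 26.9 (27), and 50% to 25% gives 28.9 (29). This is not the planned comparison, but it is a plausible origin for the number.

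So 30 is untraceable rather than refuted.

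**2. How much does the baseline rate matter?** Holding the 65% relative fall:

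| Baseline | Target | n per group |
|---|---|---|
| 52% | 18.2% | about 30 |
| 39% | 13.65% | 47 |
| 26% | 9.1% | 79 |

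The trend depends on holding the relative fall constant, which the protocol never says it does. Holding the absolute fall at 33.8 points reverses the direction: 39% to 5.2% needs about 22 per group.

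**3. The implied loss.** If 30 and 50 share a unit, 30/(1-d) = 50 gives d = 1 - 30/50 = 0.40. Losses of 10%, 20% and 30% would give 34, 38 and 43. The protocol states no d and says only approximately 30, so 50 may simply be a generous rounded target.

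**4. What the design delivers.** For 52% v 26%, power is 54% with 30 v 30, 63% with 50 v 30 and 77% with 50 v 50. At 50 v 50:

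| Fall in incidence | Power |
|---|---|
| 52% to 25% | 80% |
| 39% to 14% | 82% |
| 26% to 6% | 79% |

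The document promises no power or effect size against which these could fall short.

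**5. Is 50 v 30 in the plan?** No. Subject Information gives 50 in each group, and Endpoints closes the study when those numbers are reached. The 50 v 30 split arises only if an unstated 40% loss is assigned wholly to the intervention group.

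**The case for a change.** The case for a change is that the protocol does more than stay silent: it makes a power statement and gives a reason for the inflation that does not fit its own design. Retrospective charts have no follow-up to lose, and the in-person survey is not the delirium outcome. Sample-size inputs normally belong in a protocol, so leaving them to an analysis plan is a weak defence. The repair would be a few sentences.

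Much of this stands. Loss to follow-up is the wrong label for the historic group, and a reader cannot tell what effect the study was sized for. Three things limit its weight:

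- Some shortfall is real. Consent precedes a simulation session booked for a later date, and use of a support device after surgery is an exclusion. Historic charts may also lack delirium scores or prove ineligible on review. A margin above the calculated number is therefore sensible in both groups, whatever it is called.
- A generous margin errs on the safe side. Any inflated target tolerates loss down to its base number, so this is no particular defect of the plan.
- Recalculating at the unit's measured rate would have no stated consequence, except possibly enrolling more patients. The plan sets no rule for that.

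Whether the 50 intervention patients are counted at the session or at a recorded ICU outcome is a fair question, but it can be settled in conduct and reporting.

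**Conclusion.** No change to the plan follows. The power statement is poorly documented and its reason for 50 is loosely worded, but no figure in it is shown to be wrong. The 40% loss holds only if 30 and 50 are in the same unit, and the 50 v 30 comparison needs the further assumption that all loss falls on one group; the protocol states neither. Accrual is fixed at 50 + 50, and following the protocol as written gives the same patients, the same comparison and the same result as a version with every input spelled out.

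A reader wanting the study's sensitivity can take it from the fixed accrual: about 80% power for falls of 52% to 25%, 39% to 14% or 26% to 6%. These figures rest on an assumed two-sided 5% alpha, the normal approximation and complete outcomes in both groups. They show that only large effects are detectable, which follows from the chosen size and not from how the 30 or the 50 was explained.

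### Every control is historic and every simulation patient comes later, so the planned comparison cannot separate the simulation effect from any change over calendar time

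*Protocol*

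**What the plan says.** - **Group sizes** (Protocol, Subject Information): "Target accrual: 50 historic patients for baseline metric; 50 current intervention patients to undergo simulation session".
- **Timing of controls** (Study Design and Methods): "Baseline retrospective data will be collected on patients prior recorded prior to the start date of this IRB submission".
- **Timing of simulation patients** (same section): "prospective patients undergoing simulation session will have data recorded post IRB start date".
- **Baseline phase** (Research Question and Aims): it "will include baseline data collection over a period of 3 months".
- **Comparison** (Data Analysis): a comparative analysis of the outcome metrics "will be completed between the pre-implementation baseline data and the post-implementation intervention data".
- **Claim made for it** (Data Analysis): "This analysis will evaluate the effect of the multi-sensory ICU simulation experience on post-operative delirium in the cardiac surgical population".

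Study Design and Methods also lists the stratifiers: type of procedure, operative time, age, gender, and return to the operating room before first extubation. Outcomes come from the electronic medical record in both periods. The protocol describes no randomisation and no concurrent untreated group, and it states no limitation on the before-after comparison.

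**The concern.** The sentence in Data Analysis is causal, and the data cannot support it. No unexposed patient is planned in the later period and no exposed patient in the earlier one. Anything that alters delirium or its recording between the two periods is counted as a simulation effect. Examples are sedation or extubation practice, staffing, season, and how often CAM-ICU is charted.

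The error can go either way. A background fall in delirium would look like a benefit. Closer screening in the later period would raise recorded delirium and could conceal a real benefit. Adopting or abandoning the simulation programme could then rest on a difference that has nothing to do with it.

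This is not a detail for a separate SAP. Who is enrolled, and when, is fixed in the protocol. An SAP could add case-mix adjustment, but it could not recover a period effect from data in which period and group are the same variable.

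**Working it through.** **1. What the contrast estimates.** Let G = 1 for a simulation patient and P = 1 for the later period. Under the stated timing, G = P for every patient. Within any stratum of procedure, operative time, age, gender and return to theatre:

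later rate − earlier rate = simulation effect + period change.

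That is one observed contrast with two unknowns. In a regression, the columns for G and P are identical, so only their sum can be estimated. None of the five stratifiers carries calendar time, so stratifying leaves the identity unchanged.

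**2. Inputs for an illustration.**
- Group sizes: 50 and 50 (Subject Information).
- Control rate: 39%, the midpoint of the 26-52% range in Research Question and Aims, (26 + 52)/2.
- Test: the protocol names none. I assume a two-sided 5% level and show both the uncorrected pooled z test and Fisher's exact test.
- Drift: 0, 5, 10 or 15 points. These are assumptions; the protocol gives no figure.
- Simulation effect: none.

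The protocol has no figure of its own for this point. Its sample size of about 30, raised to 50, cannot be re-derived because the error rate, power and effect size are not given. It also does not bear on a bias.

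**3. Method.** Let a be the number of delirium cases among 50 historic patients and b the number among 50 later patients. With p = (a + b)/100,

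z = ((a − b)/50) / √(p(1 − p) × 2/50).

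For a = 20 and b = 10: p = 0.30, standard error √0.0084 = 0.0917, z = 0.20/0.0917 = 2.18, significant. For b = 11, z = 1.95, not significant. The probability of a false benefit is the sum, over all pairs with b < a and a significant result, of Bin(a; 50, p1) × Bin(b; 50, p2).

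**4. Chance of a significant false benefit.**

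| Earlier v later rate | Pooled z | Fisher exact |
|---|---|---|
| 39% v 39% | 2.6% | 1.6% |
| 39% v 34% | 7.5% | 5.0% |
| 39% v 29% | 18.0% | 13.3% |
| 39% v 24% | 36.4% | 29.2% |
| 52% v 42% | 18.3% | 13.4% |
| 26% v 16% | 23.5% | 16.8% |

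**5. More patients do not help.** For 39% v 29% with pooled z, 30 v 30 gives 12.2% and 50 v 50 gives 18.0%. A larger study detects the drift more often and still labels it a simulation effect.

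**6. The other direction.** Suppose the simulation truly lowers delirium by 20 points, from 39% to 19%. With no drift, the chance of a significant benefit is 60.6% (pooled z) or 52.5% (Fisher). If recorded delirium also rises by an assumed 10 points, the later rate is 29%, and the chance falls to the 18.0% or 13.3% in the table.

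**The case against.** **The design is declared openly.** The protocol plainly calls the groups historic and intervention, and the phases pre- and post-implementation. Confounding with time is the general limit of every before-after study, and a hypothesis may properly be causal. This stands, and a before-after study is legitimate when reported as one. What does not stand is the sentence in Data Analysis saying that the comparison evaluates the effect.

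**Drift is hypothetical.** This also stands. The protocol gives no evidence that delirium rates will change. Practitioners' concern about delirium does not show changing practice, and retrospective abstraction cannot have altered the care it records. A reader might infer that a fall in delirium would be equally well explained by period. The documents do not support that, because they say nothing about the size of any drift. They support only that the two cannot be distinguished.

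**Staff awareness.** A reader might infer that those charting CAM-ICU know the programme is running. The protocol does not say so. It describes a headset video arranged from the pre-surgical clinic, and it says only that team members from critical care and cardiothoracic surgery guided the recording.

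**The three-month phrase.** "The initial phase of this project will include baseline data collection over a period of 3 months" may refer to an admission window or to the time spent abstracting. Season is unbalanced by design only under the first reading. The main point does not depend on it.

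**Concurrent patients may already be covered.** The protocol says "Charts of all initial post cardiac surgery patients admitted directly to the ICU who meet the above criteria will be reviewed". Read alone, this could reach later patients who had no session. However, prospective data are described only for patients undergoing the session, and target accrual is 50 + 50. A concurrent group would therefore be an addition.

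**Conclusion.** The concern holds in a limited form. Group and calendar period coincide completely, so the planned comparison estimates simulation effect plus period change. It cannot by itself support the statement that it evaluates the effect of the simulation. This follows from the protocol's own timing and needs no assumption about drift.

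The size is conditional. With 50 v 50, a 39% control rate, no simulation effect and a two-sided 5% test, assumed falls of 5, 10 or 15 points give a significant false benefit in about 5-8%, 13-18% or 29-36% of studies, against about 2-3% with no drift. The range runs from Fisher's exact test to pooled z. These are scenarios, not forecasts, and drift in the other direction could hide a benefit.

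The documents do not show that drift will occur, or that period is as likely an explanation as the simulation. The study can still describe a before-after difference.

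**What to change.** 1. **Data Analysis.** Reword so that the analysis estimates a before-after difference in delirium, state that this cannot be distinguished from period change, and do not attribute it to the simulation on this comparison alone. This costs only wording and should be done whatever else is possible.
2. **Study Design and Methods.** Because the baseline is retrospective, draw the historic charts from the same calendar months as intervention accrual. Accrual ends when the sample sizes are reached, so finalise the chart selection once those months are known. This reduces seasonal imbalance but does not remove other changes between periods.
3. **Concurrent comparator.** Where record-use permission allows, abstract on the same form eligible patients operated on during the intervention period who had no session. Report concurrent unexposed v historic (an indication of drift) and simulation v concurrent unexposed, each with a confidence interval. Treat both as supportive. Do not make attribution depend on the first showing no change: in a small, self-selected group, failure to detect drift is not evidence that there was none.

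The cost is a short amendment, chart abstraction beyond the 50 + 50 target, and a less favourable conclusion. The concurrent group may be small, and patients who decline or cannot be scheduled may differ in delirium risk. No new procedure or assessment is needed.
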